3.1.3 Statistical Methods

For calculating the rate of serious adverse events after randomization, patients with insufficient follow-up will be excluded from the calculation; that is, only patients that have at least follow-up through the long term visit (120/150 day follow-up) will be included unless the subject has already had a serious adverse event. All patients with a serious adverse will be counted in the analysis. Sensitivity analyses, such as a tipping point analysis will be performed to assess the impact of the missing data, assuming extremes of either no SAEs or all SAEs for the primary endpoint, if the data support such analysis.

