	
planned surgery due to a complication, biliary obstructive symptoms, decline in patient physiologic status, or other factors that preclude surgery.
 
Group 2 (Pre-Operative Biliary Drainage with a SEMS): Patients will undergo resection after resolution of jaundice is achieved (defined as Bilirubin below 100µmol per liter), or at 4 weeks, whichever comes first.
 
 • Biliary Reintervention Visit (as needed): Timing, Reason for Biliary Reintervention, Type of Biliary Reintervention, AEs Group 1 patients who fail their treatment algorithm by requiring biliary drainage prior to surgery will receive a study SEMS. Group 2 patients who require re-stenting or placement of a stent for a new stricture, will receive a study SEMS. • Curative Intent Surgery: Assessment of Biliary Obstructive Symptoms, Laboratory Tests, Operative Details, Stent Removal, Blood Loss, Intra- and Post-Operative Transfusion, Post-Operative Course, Specimen Pathology, AEs • Transition to Palliative Management Visit (as needed): Assessment of Biliary Obstructive Symptoms, Laboratory Tests, AEs • Post-Operative Follow up Visit (30 days Post-Surgery, if applicable): Assessment of Biliary Obstructive Symptoms, Laboratory Tests, AEs • Long Term Follow-up Visit (120 days--150 days post randomization): Assessment of Biliary Obstructive Symptoms, Laboratory Tests, AEs 
Patients who undergo surgery as planned will be evaluated at 30 days post-surgery and will be followed up to 120 days after randomization.
 
Patients with delay in planned surgery may require follow up longer than 120 days to allow for a 30 day post-surgery follow up visit but follow up is not to exceed 150 days post-randomization.
 
Patients with a delay in planned surgery whose rescheduled surgery is unable to occur within 120 days will be followed up to 120 days after randomization.
 
Patients who do not undergo surgery as planned due to conversion to palliative management or patient choice will be followed up to 120 days after randomization. If patient's course of treatment requires placement of a biliary stent, stenting will be done per

--	---

	
standard of care at each institution. If a metal stent is required, a study WallFlex Biliary FC stent will be placed.

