3.1.2 Sample Size

A literature search of preoperative biliary drainage with self-expanding metal stents in patients with pancreatic or periampullary cancer yielded 8 articles with 305 patients.^{21-24, 27-31}

The following meta-analysis of the probability for pre-operative, operative and post-operative complications was done:

- A rate of 24.2% [95% CI: 13.2%, 37.2%] was calculated using the 8 articles.

The sample size was calculated for a one-sided 0.050 exact Farrington-Manning test using StatXact 9®. If the P value from the exact Farrington-Manning test is <0.05 then the *Pre-Operative Biliary Drainage with SEMS* group will be considered non-inferior to the *No Pre-Operative Biliary Drainage* group. The expected probability of complications in the *Pre-Operative Biliary Drainage with SEMS* arm and *No Pre-Operative Biliary Drainage* arm is 37.2%, which was taken from the upper limit of the 95% CI from the meta-analysis described above and from the only available Level 1 study comparing no drainage to preoperative stenting in which the complication rate was reported to be 39% in the no drainage arm.⁹ The non-inferiority margin (Δ) is 15%. Given these assumptions and a one-sided 5% significance level, $2 \times 132 = 264$ subjects will provide 80% power to reject the null hypothesis, that the *Pre-Operative Biliary Drainage with SEMS* group is inferior to the *No Pre-Operative Biliary Drainage* group.

To compensate for possible loss of subjects after enrollment and complete assessment of inclusion/exclusion criteria, an additional 10% of subjects will be enrolled, for a total of $2 \times 147 = 294$ subjects.

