4 GENERAL STATISTICAL METHODS

4.1 Analysis Sets

Primary endpoint and selected secondary endpoints will be done for the following cohorts.

Enrolled Cohort

A subject is considered “enrolled” after signing the study-specific ICF. Subjects who sign the ICF but subsequently do not meet one or more of the eligibility criteria provided in the synopsis above will be considered screen failures and excluded from the study.

Intent-to-Treat Cohort (ITT)

This cohort consists of those “enrolled” subjects who meet all inclusion/exclusion criteria and are subsequently randomized.

Per-Protocol Cohort (PP)

The per-protocol cohort is a subset of the ITT subjects who are treated per protocol after randomization (Group 1 no stent, and Group 2 received a study stent) and who had no major protocol deviations (ICH E9 definitions).

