7.3 Rules and Definitions

Binary event rates (proportions) will be reported on a per patient basis.

The last follow-up date will be the latest of the following dates for each patient: date of an adverse event, index procedure date, follow-up visit date, any stent procedure/reintervention date, surgery date, stent removal date, and device event date.

Serious Adverse Event will be defined as an adverse event that:

- Led to death
- Led to a serious deterioration in the health of the subject that either resulted in:
 - a life-threatening illness or injury, or
 - a permanent impairment of a body structure or a body function, or
 - in-patient hospitalization or prolonged hospitalization (of an existing hospitalization), or
 - medical or surgical intervention to prevent life-threatening illness or injury or permanent impairment to a body structure or a body function
- Led to fetal distress, fetal death, or a congenital abnormality or birth defect.

Note: Planned hospitalization for a pre-existing condition, or a procedure required by the protocol, without serious deterioration in health, is not considered a serious adverse event.

When calculating rates of adverse events, missing and partial dates will be handled as follows:

Partial Date Description	Action Taken
Entire onset date is missing	The procedure date will be used for the onset date.

Partial Date Description	Action Taken
The month and the day of the month are missing but the year is available	January 1 will be used for the month and day of the onset date. However, if the imputed date falls before the procedure date, then the procedure date will be used for the onset date.
Day is missing, but the month and year are available	The 1 st will be used as the day of the onset date. However, if the imputed date falls before the procedure date, then the procedure date will be used for the onset date.

Definitions of complication criteria (per van der Gaag article):

Specific PBD (ERCP, PTC) related:

- **Acute pancreatitis** Abdominal pain and a serum concentration of pancreatic enzymes (amylase or lipase) three or more times the upper limit of normal, that required more than one night of hospitalization
- **Acute cholecystitis** No suggestive clinical or radiographic signs of acute cholecystitis before the procedure and if emergency cholecystectomy is subsequently required
- **Perforation** Retroperitoneal or bowel-wall perforation documented by any radiographic technique or direct visual evidence

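### The primary SAE rate keeps early leavers who had an SAE and drops those who had none, so unequal loss between arms shifts the non-inferiority test

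*SAP*

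**What the plan says.** Section 3.1.3 sets the rule for the primary rate: "patients with insufficient follow-up will be excluded from the calculation". Only patients followed through the 120/150-day visit "will be included unless the subject has already had a serious adverse event", and every patient with an SAE is counted.

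The same section adds a safeguard: "Sensitivity analyses, such as a tipping point analysis will be performed to assess the impact of the missing data". It names the extremes of no SAEs and all SAEs among the missing, but only "if the data support such analysis".

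The decision rule is in section 3.1.2: "If the P value from the exact Farrington-Manning test is <0.05 then the" SEMS arm is declared non-inferior. The margin is 15 percentage points. Section 4.1 defines the ITT cohort as enrolled subjects "who meet all inclusion/exclusion criteria and are subsequently randomized", with no follow-up condition.

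**The concern.** For patients who leave early, the outcome decides whether they are analysed. Those with an SAE before leaving stay in, and those without are removed from the denominator. The result is neither the probability in the hypotheses of section 3.1.1 nor a rate over the ITT cohort of section 4.1.

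The trial's confirmatory claim is one p-value computed on this set. More loss from the no-drainage arm inflates the control rate more and makes a false non-inferiority finding more likely. More loss from the SEMS arm costs power. One arm is stented at day 0 and waits for jaundice to resolve or for week 4; the other goes to resection without drainage. Equal loss is possible but cannot be taken for granted.

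**Working it through.** **Inputs from the SAP (sections 1 and 3.1.2).** 37.2% expected in both arms; margin 15 points; one-sided 5% exact Farrington-Manning test; 132 per arm, raised to 147 for 10% loss; 1:1 allocation.

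**Assumed, because the SAP does not give them.** d = share of an arm lost early; f = share of leavers' SAEs that occur before they leave, taken as 0.5 to 1; loss unrelated to SAE risk; 147 per arm randomised.

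**The SAP's own figure.** An exact unconditional Farrington-Manning test with 132 per arm has 80.4% power, so the stated 80% is reproduced. 132/0.9 = 146.7, rounded up to 147. With 147 per arm and no loss, power is 84.7% and type I error at the margin is 4.5%.

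**Bias in one arm.** The rule gives an expected rate of

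rate = p(1 − d + df) / (1 − d + dpf).

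With p = 0.372:
- d = 0.10, f = 0.5: 0.3534/0.9186 = 38.5% (+1.3 points)
- d = 0.10, f = 1: 0.372/0.9372 = 39.7% (+2.5 points)
- d = 0.15, f = 0.5: 0.3441/0.8779 = 39.2% (+2.0 points)
- d = 0.15, f = 1: 0.372/0.9058 = 41.1% (+3.9 points)

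**Effect on the difference at the margin (true 52.2% vs 37.2%), 5% SEMS / 15% control loss.** For f = 0.5 the SEMS rate is 0.50895/0.96305 = 52.8%, and the expected difference is 52.8 − 39.2 = 13.7 points (unrounded inputs) instead of 15. For f = 1 it is 53.5 − 41.1 = 12.4 points.

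**Effect on the decision.** Exact test, 147 per arm; the rows with loss come from 40,000 simulated trials each. A dash means not computed.

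| Loss SEMS / control | Type I error, f = 0.5 to 1 | Power, f = 0.5 to 1 |
|---|---|---|
| none | 4.5% | 84.7% |
| 10% / 10% | 4.5% to 4.6% | 80.9% to 81.6% |
| 8% / 12% | 5.8% to 6.5% | – |
| 5% / 15% | 7.4% to 10.9% | – |
| 15% / 5% | – | 73.3% to 66.8% |

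The asymptotic form of the test shows the same pattern from a 5.4% no-loss baseline: about 8.0% to 11.5% at 5%/15%.

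**What the sensitivity analyses would show.** Take 7 SEMS and 22 control patients excluded. This is a severe case: under the model above, 22 of 147 excluded controls means 22/(147 × 0.814) = 18% loss at f = 0.5, or 22/(147 × 0.628) = 24% at f = 1. P-values are asymptotic.

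| Handling of missing | SEMS vs control | Difference (points) | p |
|---|---|---|---|
| SAP rule | 62/140 vs 50/125 | 4.3 | 0.037 (exact 0.041) |
| No SAEs | 62/147 vs 50/147 | 8.2 | 0.11 |
| All SAEs | 69/147 vs 72/147 | −2.0 | 0.002 |
| SEMS all, control none | 69/147 vs 50/147 | 12.9 | 0.36 |

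The primary rule declares non-inferiority, one named extreme agrees and the other does not. The SAP does not say what follows.

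Equal loss shows a second gap. With 49/132 in each arm and 15 missing in each, both symmetric extremes pass (p = 0.003 and 0.004). Setting SEMS-missing to SAE and control-missing to none (64/147 vs 49/147) gives p = 0.20. Symmetric extremes alone would not reveal that fragility.

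**Check of the remedy.** 6,000 trials per setting, SAEs either at constant hazard or all before day 45, loss times uniform over 120 days, Wald bound. At 5%/15% loss the present rule rejects 8.8% and 10.6% of the time at the margin. Kaplan-Meier at day 120 gives 5.6% and 5.1%, and multiple imputation 5.5% and 5.1%. At 15%/5% loss, power is 75.0% and 70.0% for the present rule, against 82.9% and 83.7% for Kaplan-Meier and 82.8% and 83.8% for imputation.

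**The case against.** - **The harm needs unequal loss, which the SAP does not predict.** At the only figure it gives, 10% overall, equal loss leaves type I error at 4.5% to 4.6%. Section 1 plans follow-up to at least 120 days in both arms, whether surgery is done as planned, delayed or not done. This stands as a limit on size. It does not make the rule unbiased, and a planned schedule does not guarantee equal completion.
- **Deaths are not lost.** Section 7.3 counts an adverse event leading to death as an SAE, so only living, SAE-free leavers are dropped. This stands, and makes heavy loss in one arm less likely.
- **The worst figures arise where the planned sensitivity analysis works best.** At f = 1 the dropped patients truly had no SAE before leaving or later, so the no-SAE extreme recovers the true rate. At 5%/15% loss, requiring both symmetric extremes to pass as well would hold type I error at 3.0% to 5.5% (asymptotic test). This is correct, but the SAP does not require it: the analyses are conditional, and section 3.1.2 decides on the primary p-value alone.
- **The 10% allowance may partly cover screen failures**, since enrolment means signing consent. Then fewer than 147 per arm would be randomised. This affects the baseline power, not the mechanism.
- **The remedies give up the pure exact test, and a fixed horizon alters the endpoint window.** This is true and is counted as a cost below.

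**Conclusion.** The concern holds. The rule is stated outright, makes inclusion depend on the outcome, and biases each arm's rate upward whenever loss is unrelated to SAE risk and some SAEs precede it. With equal loss, the effect on the comparison is negligible. A modest imbalance (8%/12%) takes type I error to 5.8% to 6.5%, and 5%/15% to between 7.4% and 10.9%; the reverse imbalance costs roughly 11 to 18 points of power (84.7 − 73.3 and 84.7 − 66.8). Loss by arm and timing of SAEs are assumptions throughout. The planned sensitivity analyses lessen the problem but do not correct the primary estimate or bind the conclusion. This should be fixed before analysis.

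**What to change.** Amend section 3.1.3 so that the primary analysis includes all randomised patients and uses their partial follow-up, by one of two routes:

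1. **Multiple imputation**, which keeps the patient-specific window. Impute SAE status for event-free early leavers by arm and time of loss, apply the Farrington-Manning comparison to each completed data set, and pool.
2. **Kaplan-Meier SAE risk at a stated fixed day**, for example day 120, comparing the upper one-sided 95% bound of the difference with 15 points. A fixed day is needed because the window varies by patient; section 1 says "follow up is not to exceed 150 days post-randomization". Censoring can build on section 7.3 ("The last follow-up date will be the latest of the following dates for each patient"). That list includes adverse event dates, so a non-serious event can extend a patient's apparent follow-up; the SAP should confirm that SAE status is known up to the date used.

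Under either route:
- keep the present rule as a sensitivity analysis;
- make the tipping-point analysis unconditional;
- vary the two arms separately, including missing SEMS as SAE with missing control as no SAE;
- state how a discordant result affects the non-inferiority conclusion.

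**Cost.** SAP wording and some programming; no extra patients or data, and the sample size is unchanged. The primary test is no longer purely exact. Both routes assume that loss is unrelated to later SAE risk given arm and time, which is why the tipping-point grid is needed. A day-120 horizon leaves later SAEs in delayed-surgery patients to a supportive analysis; route 1 avoids that. If the sponsor keeps the present primary rule, the least that should be done is to make the sensitivity analyses mandatory, arm-specific and tied to the decision.

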4 GENERAL STATISTICAL METHODS

4.1 Analysis Sets

Primary endpoint and selected secondary endpoints will be done for the following cohorts.

Enrolled Cohort

A subject is considered “enrolled” after signing the study-specific ICF. Subjects who sign the ICF but subsequently do not meet one or more of the eligibility criteria provided in the synopsis above will be considered screen failures and excluded from the study.

Intent-to-Treat Cohort (ITT)

This cohort consists of those “enrolled” subjects who meet all inclusion/exclusion criteria and are subsequently randomized.

Per-Protocol Cohort (PP)

The per-protocol cohort is a subset of the ITT subjects who are treated per protocol after randomization (Group 1 no stent, and Group 2 received a study stent) and who had no major protocol deviations (ICH E9 definitions).

5 ADDITIONAL DATA ANALYSES

5.1 Secondary Endpoints

1. Adverse events: rate, severity, seriousness, relatedness to stent or endoscopic or surgical procedure, impact on time of surgery, length of hospitalization and ICU stay
2. Time to surgery
3. Curative Intent Surgery details pertaining to intraoperative assessment of resectability, surgical resection and reconstruction techniques
4. Intraoperative blood loss and blood transfusions, duration of surgery
5. Biliary obstructive symptoms assessment (Week 2, surgery/transition to palliation, 30 day post-operative follow up and 120 day follow up)
6. Improvement of LFT levels as relative to baseline (Week 2, surgery/transition to palliation, 30 day post-operative follow up and 120 day follow up)
7. Stent placement success: ability to deploy the stent in satisfactory position across the stricture (Group 2)
8. Stent removal success: successful SEMS removal, either *en bloc* at time of surgery or endoscopically prior to surgery without stent removal related SAEs
9. Number, type, reason and timing of biliary re-interventions and time to first re-intervention.
10. Number and duration of hospital and ICU admissions

5.2 Baseline Data

Baseline data will be summarized. Subject demographics, clinical history, risk factors, LFTs, tumor diagnosis, and obstruction symptoms will be summarized using descriptive statistics (e.g., mean, standard deviation, n, minimum, maximum) for continuous variables and frequency statistics for discrete variables.

5.3 Post-Procedure Endpoints

Post-procedure information will be collected at regularly scheduled follow-up examinations as detailed in the clinical study event schedule and will be summarized using descriptive statistics for continuous variables (e.g., mean, standard deviation, n, minimum, maximum) and frequency tables or proportions for discrete variables.

5.4 Subgroup Analyses

The subgroup analyses will include tabulating the primary endpoint and select secondary endpoints by gender.

5.5 Justification of Pooling

The analyses will be presented using pooled data across institutions. An analysis of the poolability will be made using logistic regression for binary outcomes, proportional hazards regression for time-to-event outcomes, or analysis of variance for continuous outcomes, to assess differences between study institutions and to justify pooling data across institutions.

5.6 Multivariable Analysis

Univariate and multivariate analyses will be performed to assess possible predictors of the rate of serious adverse events. Possible predictors may include any but not limited to demographic/baseline data and medical history data. Factors from the univariate model with $p \leq 0.20$ will also be modeled multivariately using a stepwise procedure in a generalized linear model or Cox proportional hazards regression model. The significance thresholds for entry and exit into the model will be set to $p < 0.10$.

5.7 Analysis of LFT's and Obstruction symptoms

For analysis of LFT's and obstruction symptoms, a paired t-test and McNemar's Test will be used to test differences from baseline. The data will also be analyzed using a generalized linear model, including treatment group and baseline covariates as predictors. Interactions between time and treatment group will be explored. Other possible predictors may include any but not limited to demographic/baseline data and medical history data. Different correlation structures will be fit to determine the best model fit.

5.8 Analysis of Impact of Adverse Events on Endpoints

For an analysis on the effect of the adverse events impact on time of surgery, length of hospitalization, and ICU stay, subjects with and without AEs will be analyzed to determine if any differences occur. Appropriate testing will be done to determine this, i.e. a 2x2 ANOVA analysis with a treatment interaction.

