- **Stent Occlusion** Recurring obstructive jaundice with necessary stent replacement

Specific surgery related:

- **Pancreaticojejunostomy leakage** Drain output of any measurable volume of fluid on or after postoperative day 3 with an amylase content greater than 3 times the serum amylase activity, graded according to clinical course (ISGPS grade A, B, C), or direct visual evidence of defect at anastomosis
- **Delayed gastric emptying** Gastric stasis requiring nasogastric intubation for 10 days or more, or the inability to tolerate a regular (solid) diet on or before the fourteenth postoperative day, not due to sequelae of intra-abdominal complications (i.e. abscess, anastomotic leakage)
- **Biliary leakage** Bilirubin in abdominal drain or dehiscence found at laparotomy
- **Gastro/-duodenojejunostomy leakage** Conclusive radiographic or direct visual evidence of a defect of the anastomosis
- **Intra-abdominal abscess formation** Intra-abdominal fluid collection with positive cultures identified by ultrasonography or computed tomography, associated with persistent fever and elevations of white blood cells
- **Wound infection** Requiring intervention otherwise considered as minor complication
- **Portal Vein Thrombosis** Conclusive radiologic evidence of thrombosis

Following either procedure:

- **Cholangitis** Elevation in temperature more than 38°C, thought to have a biliary cause, without concomitant evidence of acute cholecystitis, requiring intervention
- **Hemorrhage** Bleeding after the index procedure requiring transfusion of ≥ 4 units of packed cells within a 24-hour period, or leading to relaparotomy/intervention
- **(Emergency) (re)laparotomy** Any (other) reason following either preoperative biliary drainage or another surgical procedure
- **Pneumonia** Pulmonary infection with radiological confirmation and requiring antibiotic treatment
- **Mortality** In-hospital death, due to protocol complications or any cause, including progression of disease, within the study period

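### Section 5.8 tests the impact of AEs on hospital and ICU stay by comparing subjects with and without an AE, but AE status itself depends on length of stay, so the AE effect can be significant when AEs cost no days

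*SAP*

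**What the plan says.** Section 5.8 states a causal aim: "For an analysis on the effect of the adverse events impact on time of surgery", length of hospitalisation and ICU stay. The method is a comparison by AE status: for time of surgery, "length of hospitalization, and ICU stay, subjects with and without AEs will be analyzed to determine if any differences occur", by appropriate testing such as "a 2x2 ANOVA analysis with a treatment interaction". This is the only method the SAP gives for the part of secondary endpoint 1 that concerns "impact on time of surgery, length of hospitalization and ICU stay" (section 5.1).

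The section does not say when an AE must start relative to the stay or to surgery. It sets no landmark, no time-dependent AE status and no allowance for time at risk. Data run to 120 days after randomisation or 30 days after surgery, whichever is later (section 2), so well past a typical discharge.

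Some event definitions in section 7.3 contain a duration of care. Acute pancreatitis needs pain and raised enzymes "that required more than one night of hospitalization". Delayed gastric emptying is "Gastric stasis requiring nasogastric intubation for 10 days or more", or failure to tolerate solid food by postoperative day 14. Separately, secondary endpoint 10 covers "Number and duration of hospital and ICU admissions".

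**The concern.** The question is what AEs cost in hospital and ICU days. The comparison answers it only if AE status is unaffected by the stay. Three features of the plan work against that.

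- **Exposure.** A patient who stays longer is under observation in hospital for longer. If AEs occur or are detected more often per day there than at home, a long stay makes it more likely that the patient joins the AE group.
- **Definition.** For pancreatitis and delayed gastric emptying, time in care is part of what makes the event count.
- **Order in time.** An AE after discharge puts a patient in the AE group although the stay was already complete. Likewise, an AE after surgery cannot have delayed that surgery, and a longer wait gives more time for a preoperative AE.

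A small p-value from this ANOVA would be read as evidence that AEs prolong stay. Section 2 foresees use of these analyses in presentations and manuscripts, where that reading would be hard to correct.

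**Working it through.** Section 5.8 contains no figure to reproduce. The check asks how often the planned ANOVA rejects when every AE costs zero days and treatment has no effect. A valid test rejects in about 5% of trials.

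**Inputs from the SAP:** 264 patients (2 × 132, section 3.1.2), 1:1 allocation, a 120-day window, and a 2x2 ANOVA with interaction. **Assumed, not in the documents:** log-normal stay L with median 14 days and log-SD 0.45; in-hospital AE hazard h of 0.02 to 0.05 per day; ratio r of in-hospital to out-of-hospital hazard; two-sided 0.05.

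**Formula.** The probability of at least one AE is

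P(AE) = 1 − exp{−[h·L + (h/r)(120 − L)]}.

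The exponent equals 120h/r + h(1 − 1/r)·L. At r = 1 the term in L vanishes and AE status does not depend on stay. For any r above 1, P(AE) rises with L although AEs add no days.

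**Example, h = 0.035, stays of 10 and 20 days.**
- r = 5: the exponent is 0.84 + 0.028·L, that is 1.12 and 1.40, so P(AE) is 67% and 75%.
- AEs only in hospital: the exponent is 0.035·L, that is 0.35 and 0.70, so P(AE) is 30% and 50%.

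**Simulated rejection of the AE main effect.** The second column uses the inputs above. The third uses log-SD 0.5, with hazards set so that about half the patients have an AE, and adds the spurious difference in mean stay.

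| In-hospital ÷ out-of-hospital AE rate | h 0.02 to 0.05, log-SD 0.45 | About 50% with an AE, log-SD 0.5 |
|---|---|---|
| 1 | about 5% or less | 5.1%, 0.0 days |
| 2 | about 3% to 10% | 9.5%, +0.7 days |
| 5 | about 40% to 46% | 47%, +1.9 days |
| 10 | 67% to 85% | 81%, +2.9 days |
| AEs only in hospital | 94% to 100% | 100%, +5.2 days |

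The lowest values in the second column arise because almost everyone has an AE. At r = 1 and h = 0.05, P(AE) = 1 − exp(−6) = 99.8%, which leaves fewer than one patient in 264 without an AE (264 × 0.0025 = 0.7).

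**Stay prompting the record.** In a separate check with a two-sample t-test, 40% of patients had an AE unrelated to stay, and a share of stays over 21 days also had an event recorded (log-SD 0.5). Shares of 0%, 25%, 50% and 100% gave rejection of 4%, 35%, 88% and 100%.

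**Interaction.** With equal arms and the inputs of the second column, the AE-by-treatment interaction was rejected in about 3% to 8% of trials, close to nominal.

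**The case against.** The strongest reply is that the size of the problem rests on a ratio the documents do not give. AEs are collected for 120 days or more, and at equal rates in and out of hospital the test keeps its level. This stands. A reader might infer that the test will report an impact whether or not there is one. The documents do not support that: rejection of 94% or more belongs to the extreme case in which no AE occurs after discharge.

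Three other strong readings also fail.

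- Section 7.3 makes an event serious if it led to "in-patient hospitalization or prolonged hospitalization (of an existing hospitalization), or" other listed outcomes, so one might say that AE patients have longer stays by definition. But section 5.8 splits on AEs, not SAEs. The criterion decides seriousness, not membership of the AE group, and acts only indirectly, where a long stay prompts an event record.
- One might say that the interaction inherits the bias. A bias equal in both arms creates no interaction, and none was seen. Unequal arms were not examined.
- Early deaths and patients never operated on complicate the comparison, but nothing in the SAP fixes the direction or size of their effect.

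It is also fair that section 5.8 is a supportive analysis with no alpha of its own. That limits the consequence but does not make the comparison answer its question.

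**Conclusion.** The point holds in limited form. The planned comparison cannot separate days caused by AEs from AEs that accompany long stays, and its false-positive rate exceeds 5% by an amount the documents do not determine. Under the stated assumptions the excess is small at a rate ratio of 2 and large at 5 or more. A higher AE or detection rate in hospital is plausible around pancreaticoduodenectomy, but it is an assumption. The days in the table are likewise illustrations, not estimates for this trial.

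For time of surgery the fault follows from the order of events and was not simulated. The point is worth correcting before analysis, but it concerns part of one secondary endpoint. The non-inferiority test and its sample size are untouched.

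**What to change.** Replace the with/without-AE ANOVA for these outcomes by one of the following.

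1. **Time-dependent AE status.** For example, use a multistate or Cox model for time to discharge, with AE onset as a time-varying covariate and death as a competing event. State which admission it covers, and treat ICU stay in the same way. For time to surgery, use preoperative AEs only, also as time-dependent.
2. **Description only.** Tabulate stay by AE status and arm, without a test and without words such as effect or impact.

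In either case, add a comparison of hospital and ICU days by randomised arm in the ITT cohort, from endpoint 10 data. Randomisation protects that comparison, but it answers a different question (what the strategy costs, not what AEs cost), so it does not replace option 1 or 2.

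Two tempting repairs should be avoided. Counting only AEs with onset during the stay recreates the in-hospital-only case, the worst in the table. Summing the days attributed to each AE needs data that the SAP does not show to be collected, and overlapping AEs could be counted twice.

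The cost is SAP wording, a little more programming and the loss of a simple p-value. Section 7.3 already presumes AE onset and surgery dates. Admission and discharge dates should be confirmed, because the SAP lists only number and duration of admissions.
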